6.5 Dose modification

Dose modifications of the IMP are permitted in order to maintain the platelet counts between $\geq 50 \times 10^9/L$ and $\leq 150 \times 10^9/L$ (Table 1-1 and Figure 1-1).

Dose modifications or temporary discontinuation of the IMP treatment are permitted if serum IgG value is $< 1g/L$ (Section 10.25).

In the event of treatment-related AEs, other than those that meet the IMP discontinuation criteria (as defined in Section 7.1) a dose reduction is permitted. Treatment-related AEs due to which dose modifications are recommended may include, but are not limited to:

- Moderate to severe headaches
- Severe vomiting and diarrhea
- Moderate to severe toxicities (Grade 2 and above, as defined by Common Terminology Criteria for Adverse Events version 5.0) for which rozanolixizumab cannot be excluded as a cause

6.6 Treatment after the end of the study

Study participants (regardless of whether they receive rescue therapy), upon completion of the Treatment Period and if fulfilling the eligibility criteria, will be given the opportunity to enroll into the OLE study, TP0004.

In case the enrollment into TP0004 is not conducted at Week 25 (Visit 27), a visit window of +3 days will be granted; therefore, rollover into TP0004 needs to be completed +3 days after Week 25 at the latest.

For study participants not enrolling into the OLE study, there are no plans for continued provision of rozanolixizumab after the end of the study. The participant should discuss any alternative treatment options (if needed after the study) with their healthcare provider.

[figure not shown]
7 DISCONTINUATION OF IMP AND PARTICIPANT DISCONTINUATION/WITHDRAWAL

7.1 Discontinuation of IMP

7.1.1 Liver chemistry stopping criteria

[figure not shown]
Discontinuation of study treatment for abnormal liver function should be considered by the investigator when a study participant meets one of the conditions outlined in [Figure 7-1](#) and [Figure 7-2](#), or if the investigator believes that it is in the best interest of the participant.

Figure 7-1: Liver chemistry stopping criteria and increased monitoring algorithm

ALT=alanine transaminase; AST=aspartate aminotransferase; INR=international normalized ratio; SAE=serious adverse event; ULN=upper limit of normal

Figure 7-2: Liver chemistry increased monitoring algorithm with continued study intervention for participants with ALT $\geq 3xULN$ but $< 8xULN$

ALT=alanine transaminase; AST=aspartate aminotransferase; bili=bilirubin; INR=international normalized ratio; SAE=serious adverse event; ULN=upper limit of normal

Specific assessments and follow-up actions for potential drug-induced liver injury (PDILI) are provided in Appendix 6, Section 10.6.

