7.2 Participant discontinuation/withdrawal from the study

Study participants are free to withdraw from the study at any time, without prejudice to their continued care. Participants who withdraw from the study should complete the EOS Visit.

A study participant may also be withdrawn from the study at any time at the discretion of the investigator for safety, behavioral, compliance, or administrative reasons.

If the study participant withdraws consent for disclosure of future information, the sponsor may retain and continue to use any data collected before such a withdrawal of consent.

If a study participant withdraws from the study, he/she may request destruction of any samples taken and not tested, and the investigator must document this in the site study records.

See the Schedule of Activities (Section 1.3) for data to be collected at the time of study discontinuation and follow up and for any further evaluations that need to be completed.

Study participants **must** be withdrawn from the study and permanently discontinued from IMP if any of the following events occur:

1. Study participant withdraws his/her consent.
2. Study participant takes prohibited concomitant medications as defined in this protocol.
3. Study participant meets the mandatory IMP discontinuation criteria as per Section 7.1.1, Section 7.1.2 or Section 7.1.3.

4. There is confirmation of a pregnancy during the study, as evidenced by a positive pregnancy test.
5. The sponsor or a regulatory agency requests withdrawal of the study participant.

Study participants who withdraw from the study or permanently discontinue IMP during the Treatment Period should complete the assessments outlined for the EW Visit, enter the SFU Period and complete the EOS Visit.

Investigators should contact the Medical Monitor, whenever possible, to discuss the withdrawal of a participant in advance. Study participants who are withdrawn will not be replaced.

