10.6 Appendix 6: Liver safety – suggested actions and follow-up assessments

Study treatment, including all concomitant medications and herbal supplements that are not medically necessary, should be discontinued immediately in study participants with suspected PDILI. These study participants must be assessed thoroughly and followed up closely during the Treatment Period for confirmation of PDILI. Because study participants in TP0003 will be provided the chance to enroll in the OLE study TP0004 upon completion of TP0003, if PDILI is confirmed, these study participants must not be enrolled in the OLE study TP0004.

Investigators should attempt to obtain information on study participants to complete the final evaluation.

Study participants with PDILI should not be withdrawn from the study until investigation and monitoring are complete. All results of these evaluations and observations, as well as the reason(s) for study participant withdrawal (if applicable, eg, withdrawal of consent), must be recorded in the source documents. The eCRF must document the primary reason for study withdrawal in such a case.

A specific monitoring plan must be agreed between the UCB study physician and the investigator for study participants who have ALT >5 ULN. The monitoring plan should include any necessary follow-up assessments (until resolution of the abnormal lab values).

Phase 3-4 liver chemistry stopping criteria are designed to assure participant safety and to evaluate liver event etiology ([Table 10-3](#)).

Phase 3-4 liver chemistry increased monitoring criteria with continued IMP are designed to assure participant safety and to evaluate liver event etiology ([Table 10-4](#)).

Table 10-3: Phase 3-4 liver chemistry stopping criteria and follow-up assessments

Liver Chemistry Stopping Criteria	
ALT-absolute	ALT ≥8xULN
ALT Increase	ALT ≥5xULN but <8xULN persists for ≥2 weeks ALT ≥3xULN but <5xULN persists for ≥4 weeks
Bilirubin^{a b}	ALT ≥3xULN and bilirubin ≥2xULN (>35% direct bilirubin)
INR^b	ALT ≥3xULN and international normalized ratio (INR) >1.5, if INR measured
Cannot Monitor	ALT ≥5xULN but <8xULN and cannot be monitored weekly for ≥2 weeks ALT ≥3xULN but <5xULN and cannot be monitored weekly for ≥4 weeks
Symptomatic^c	ALT ≥3xULN associated with symptoms (new or worsening) believed to be related to liver injury or hypersensitivity
Suggested Actions and Follow-Up Assessments	
Actions	Follow-Up Assessments

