
 • Immediately discontinue IMP. • Report the event to UCB within 24 hours. • Complete the liver event electronic Case Report Form (eCRF), and complete a serious adverse event (SAE) data collection tool if the event also met the criteria for an SAE.^b • Perform liver chemistry follow-up assessments. • Monitor the participant until liver chemistry test abnormalities resolve, stabilize, or return to Baseline (see MONITORING). • Do not restart/rechallenge participant with IMP unless allowed per protocol and UCB approval is granted. 
If restart/rechallenge not allowed per protocol or not granted, permanently discontinue IMP and continue participant in the study for any protocol specified follow up assessments. Consider the need for a toxicology screening.
 
MONITORING: For bilirubin or INR criteria:
	
 • Viral hepatitis serology^d • Obtain INR and recheck with each liver chemistry assessment until the transaminases values show downward trend • Only in those with underlying chronic hepatitis B at study entry (identified by positive hepatitis B surface antigen), quantitative hepatitis B deoxyribonucleic acid (DNA) and hepatitis delta antibody^e • Obtain blood sample for pharmacokinetic (PK) analysis as soon as feasible after the most recent dose^f • Serum creatine phosphokinase (CPK) and lactate dehydrogenase (LDH) • Fractionate bilirubin, if total bilirubin ≥ 2xULN • Obtain complete blood count with differential to assess eosinophilia • Record the appearance or worsening of clinical symptoms of liver injury, or hypersensitivity, on the adverse event (AE) report form

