
 Repeat liver chemistry tests (include ALT, aspartate transaminase [AST], alkaline phosphatase, bilirubin) and perform liver event follow-up assessments within 24 hours. Monitor participant twice weekly until liver chemistry test abnormalities resolve, stabilize, or return to Baseline. A specialist or hepatology consultation is recommended. 
For all other criteria
 
 Repeat liver chemistry tests (include ALT, AST, alkaline phosphatase, bilirubin) and perform liver chemistry follow-up assessments within 24 to 72 hours. Monitor participants weekly until liver chemistry abnormalities resolve, stabilize, or return to Baseline. 	
 Record use of concomitant medications (including acetaminophen, herbal remedies, and other over-the-counter medications) on the concomitant medications eCRF. Record alcohol use on the liver event alcohol intake eCRF Exclude pregnancy 
For bilirubin or INR criteria:
 
 Anti-nuclear antibody, anti-smooth muscle antibody, Type 1 anti-liver kidney microsomal antibodies, and quantitative total immunoglobulin G (IgG) or gamma globulins ^g Serum acetaminophen concentration and serum acetaminophen adduct assay (where available) for assessing the potential acetaminophen contribution to liver injury. Liver imaging (ultrasound, magnetic resonance, or computerized tomography) and/or liver biopsy to evaluate liver disease; complete Liver Imaging and/or Liver Biopsy eCRFs
---	---

^a Serum bilirubin fractionation should be performed if testing is available. If serum bilirubin fractionation is not immediately available, discontinue IMP if ALT $\geq 3xULN$ and bilirubin $\geq 2xULN$. Additionally, if serum bilirubin fractionation testing is unavailable, **record the absence/presence of detectable urinary bilirubin on dipstick**, which is indicative of direct bilirubin elevations suggesting liver injury.

^b All events of ALT $\geq 3xULN$ and bilirubin $\geq 2xULN$ (>35% direct bilirubin) or ALT $\geq 3xULN$ and INR >1.5 may indicate severe liver injury (**possible ‘Hy’s Law’**) and **must be reported as an SAE (excluding studies of hepatic impairment or cirrhosis)**. The INR measurement is not required, and the stated threshold value will not apply to participants receiving anticoagulants.

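### Protocol 7.1.1 leaves stopping IMP for a liver stopping criterion to the investigator's consideration, while 7.2 item 3 treats the 7.1.1 criteria as mandatory and Table 10-3 orders an immediate stop

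*Protocol*

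**What the plan says.** Four places in the current protocol bear on whether IMP stops once a liver stopping criterion is met.

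- **Section 7.1.1.** "Discontinuation of study treatment for abnormal liver function should be considered by the investigator" when a participant meets a condition in Figure 7-1 or Figure 7-2, or when the investigator believes stopping is in the participant's best interest. Figure 7-1 is captioned as holding the stopping criteria and a monitoring algorithm. Figure 7-2 is captioned "Liver chemistry increased monitoring algorithm with continued study intervention for participants with ALT" of at least 3×ULN but below 8×ULN. The section ends: "Specific assessments and follow-up actions for potential drug-induced liver injury (PDILI) are provided in Appendix 6, Section 10.6".
- **Section 7.2, item 3.** Under a lead-in that uses *must*, the listed event is: "Study participant meets the mandatory IMP discontinuation criteria as per Section 7.1.1, Section 7.1.2 or Section 7.1.3". The consequence is study withdrawal and permanent discontinuation of IMP.
- **Appendix 6 (10.6), Table 10-3.** The first action for the stopping criteria is "Immediately discontinue IMP". Footnote a adds: "If serum bilirubin fractionation is not immediately available, discontinue IMP if ALT" is at least 3×ULN and bilirubin is at least 2×ULN. However, the appendix title describes its content as "suggested actions and follow-up assessments", and the action block of Table 10-3 carries the same label. The opening text of the appendix says study treatment "should be discontinued immediately in study participants with suspected PDILI".
- **Appendix 6, Table 10-4.** IMP can continue in the increased-monitoring categories. A participant who later meets a stopping criterion is to be handled as 7.1.1 describes.

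**The concern.** A stopping criterion should give one answer wherever the site looks it up. Here the section that owns the criterion speaks of considering a stop, the withdrawal section calls the same section's criteria mandatory, and the appendix table gives a direct order under a heading that softens it.

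What is at stake is consistent hepatic-safety instruction. Table 10-3 includes ALT of at least 8×ULN, and ALT of at least 3×ULN combined with bilirubin of at least 2×ULN or with INR above 1.5. Its footnote b identifies those two combinations as possible Hy's Law. A site acting on the 7.1.1 sentence alone could treat the stop in such a case as optional. A site that followed the reference to Appendix 6 would stop.

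**Working it through.** No arithmetic applies, and the plan states no figure to reproduce. The check sets the texts side by side for one question: a participant meets a Table 10-3 stopping criterion; must IMP stop?

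| Place | Answer on its face |
|---|---|
| 7.1.1, operative sentence | Investigator considers it |
| 7.2 item 3 | Yes, mandatory and permanent |
| Table 10-3, first action | Yes, immediately |
| Table 10-3 action heading and Appendix 6 title | The actions are suggestions |

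**Step 1: is the 7.1.1 sentence really about stopping cases?** Yes. It names the conditions of Figure 7-1, whose caption refers to stopping criteria, and the section has the same title. It also names Figure 7-2, whose caption refers to continued treatment. One discretionary verb therefore covers both kinds of case.

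**Step 2: is discretion the general style of Section 7.1?** No. For participants who meet its listed QTc criteria, 7.1.2 says they will discontinue IMP. Section 7.1.3 says participants must permanently discontinue for its listed events, although its infection item leaves some room for judgment. Of the three sections that 7.2 item 3 cites, only 7.1.1 has no firm verb in its visible text.

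**Step 3: does Appendix 6 settle it?** Only partly. The action in Table 10-3 is firm and footnote a repeats it for one sub-case, but the heading above it weakens it. Table 10-4 then sends a worsening participant back to 7.1.1, so a site following that path arrives at the discretionary sentence.

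**Step 4: could the missing figures resolve it?** Figure 7-1 may well direct a stop, and its absence from this copy is no fault of the plan. If it does, it would contradict the sentence that introduces it, and that sentence would still need changing.

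**Step 5: who was exposed?** The Amendment 3 summary of changes lists item 3 as an addition to 7.2. SAP 2.3 reports 33 participants randomized under previous protocol versions, and SAP 3.2.4 says none were randomized or treated under Amendment 3. The conflict between 7.1.1 and 7.2 item 3 therefore governed 0 treated participants. The documents give no count of liver events and do not show the full earlier text of 7.1.1.

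**The case against.** The strongest reply is that no site reads one sentence in isolation. The conditions sit in figures that are not shown here and may be firmer. Section 7.1.1 itself refers to Appendix 6, which separates stop cases (Table 10-3) from continue cases (Table 10-4) and directs a stop. Sites also do not act alone: stopping events are reported to the sponsor within 24 hours, and monitoring cases go to the Medical Monitor within 24 hours. All of this stands, and it is why the point is minor. It does not remove the mismatch, because the governing sentence remains softer than the table it relies on.

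Three stronger readings are tempting, and the documents do not support them.

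- A reader might infer that 7.2 item 3 forces a stop in the increased-monitoring cases too, because they share 7.1.1. The word *mandatory* in item 3 more naturally selects the stopping cases within the cited sections. The Figure 7-2 caption and the title of Table 10-4 both say that treatment continues.
- A reader might count firm against soft phrases across the protocol. Such a tally measures nothing. The phrases overlap, and some are off the point: the Table 10-1 footnote on required actions covers monitoring events as well as stopping events.
- A reader might take Section 6.5, which refers to the discontinuation criteria of Section 7.1 when permitting dose reductions, as evidence that the liver stop is firm. Section 7.1 also contains temporary holds, so the reference says nothing about how firm the liver stop is.

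**Conclusion.** The point holds as a minor drafting inconsistency in current safety text. Section 7.1.1 as written makes stopping for a liver stopping criterion discretionary, in conflict with 7.2 item 3 and with the action in Table 10-3. The label on Table 10-3 adds to the ambiguity.

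A reader might go further and infer that participants were left on drug unsafely or that results were affected. Nothing in the documents shows either. No participant was randomized or treated under Amendment 3, no liver-event count is given, and no endpoint effect is claimed.

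Confidence is medium. The conclusion rests on the visible text, and Figure 7-1 could contain a firm instruction. That would make a wrong action by a site less likely but would leave the 7.1.1 sentence out of line.

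There is one related loose end. Section 7.2 requires study withdrawal without saying when, whereas 10.6 holds withdrawal back in PDILI cases until investigation and monitoring are finished. The specific rule can be read as governing, and 7.2 also provides for the EW, SFU and EOS visits, so this is an optional tidy-up.

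**What to change.** 1. In 7.1.1, replace the single sentence with three statements: IMP must be discontinued immediately when a Figure 7-1/Table 10-3 stopping criterion is met; IMP may continue with weekly monitoring in the Figure 7-2/Table 10-4 cases; in any other case, discontinuation should be considered if the investigator judges it to be in the participant's best interest. The discretionary wording should not remain attached to the Table 10-4 cases, where IMP can continue.
2. In Table 10-3, label the stop action as required. The work-up items can keep their present label.
3. Optionally, have 7.2 item 3 name the liver stopping criteria explicitly, and add that for PDILI, study withdrawal waits until investigation and monitoring are complete, as 10.6 says.

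The cost is a few lines of text, with no change to visits, data or sample size. SAP Section 1 records the sponsor's decision to terminate the study, so the benefit lies in the text of record and in any later protocol that reuses this language.

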7.1.2 QTc stopping criteria

If a clinically significant finding is identified (including but not limited to: changes from Baseline in QT interval corrected using Fridericia's formula) after enrollment, the investigator or qualified designee will determine if the study participant can continue in the study and if any change in participant management is needed. This review of the ECG printed at the time of collection must be documented. Any new clinically relevant finding should be reported as an AE.

A study participant who meets the bulleted criteria based on the ECG readings will discontinue IMP and move into the SFU Period. The study participant should be referred to a specialist (ie, cardiologist) and managed as per local guidance.

- QTc >500 msec OR uncorrected QT >600 msec
- Change from Baseline of QTc >60 msec

For study participants with underlying bundle branch block, follow the discontinuation criteria listed below:

Baseline QTc with Bundle Branch Block	Discontinuation QTc Threshold with Bundle Branch Block
<450 msec	>500 msec
450 to 480 msec	≥530 msec

7.1.3 Discontinuation of IMP due to other adverse events or medical condition

Study participants **MUST permanently discontinue IMP** and move into the SFU Period if any of the following events occur:

- Study participant has a significant infective episode including but not limited to: bacteremia or sepsis, infectious meningitis, osteomyelitis, septic arthritis, complicated pneumonia or visceral abscess which may or may not result in hospitalization. This list is not intended to be all inclusive, and the investigator is expected to apply his/her judgment on continuing IMP based on the clinical situation at hand (see Appendix 25, Section 10.25).
- Study participant has new onset or recurrent neoplastic disease (except for superficial basal or squamous cell carcinoma of the skin not requiring targeted biological therapy, chemotherapy or radiation).
- Study participant has an AE of severe or serious hypersensitivity, infusion related reaction (see Appendix 24, Section 10.24) or anaphylaxis requiring corticosteroid and/or epinephrine therapy (see Appendix 21, Section 10.21) (Sampson et al, 2006).
- Study participant has a serious AE of headache or GI disturbance that is considered related to the IMP in the opinion of the investigator; or recurrent severe AE of headache (see Appendix 22, Section 10.22) or GI disturbance that is considered related to the IMP in the opinion of the investigator (See Appendix 23, Section 10.23).
- Study participant has a life-threatening bleeding event.
- Study participant has an AE of arterial or venous thromboembolic event (eg stroke, myocardial infarction, pulmonary embolism, deep vein thrombosis).
- Study participant has evidence suggestive of potential TB infection (eg, exposure), and further examinations result in a diagnosis of active TB, LTBI, or NTMBI (see Section 8.2.5).
- If a NTMBI is identified during the study, the same withdrawal procedures as those used for an active TB infection identified during the study should be followed.

Study participants who permanently discontinue IMP during the Treatment Period and hence are withdrawn from the study should complete the assessments outlined for the Early Withdrawal (EW) Visit and enter the SFU Period.

7.1.4 Temporary IMP discontinuation

Study participant **MUST temporarily discontinue IMP** if any of the following events occur:

1. Thrombocytosis (platelet count of $\geq 400 \times 10^9/L$).

2. In the event of confirmed COVID-19 infection (eg, signs/symptoms such as fever, cough, shortness of breath), or known exposure sufficient to necessitate testing or self-imposed quarantine.

The IMP may be restarted if:

- a. COVID-19 test is negative, and signs and symptoms have resolved
- b. If test is not available, resolution of signs and symptoms and 14 days have passed since initial presentation of the clinical signs/symptoms.
- c. If asymptomatic, 14 days have elapsed since known exposure.

Study participant **MAY temporarily discontinue IMP** if any of the following events occur:

1. A severe AE of headache that is considered related to the IMP in the opinion of the investigator (Section 10.22)
2. A splenectomised study participant develops a (persistent or re-occurring) nonserious infection, as per investigator's decision (Section 10.25)
3. Total serum IgG value is <1g/L as per investigator's decision. As IMP treatment is administered weekly, the decision to temporarily hold the treatment should be determined based on the most recently available total IgG value. As the IgG, IgG subtypes, albumin and total protein levels will be blinded to both the study site personnel and the clinical team at the sponsor and CRO, unblinded Medical Monitors will be monitoring the IgG levels and will alert the investigator in case of decreases <1g/L. Additionally, guidance for investigators on management of infections can be found in Appendix 25, Section 10.25.

